Intralymphatic immunotherapy in pollen-allergic young adults with rhinoconjunctivitis and mild asthma: A randomized trial

Date: 24/11 2019.

Study outline

All eligible allergic patients at the allergy clinics at the Karolinska University Hospital in Solna/Huddinge, Stockholm, Sweden, were screened and enrolled in the study during the inclusion period January 1, 2013, and December 31, 2015. Inclusion criteria were age 16 to 45 years, confirmed allergy to birch and/or timothy grass pollen together with rhinoconjunctivitis and mild asthma (controlled asthma [asthma control test score > 19] and a positive methacholine challenge), and otherwise healthy. Exclusion criteria were troublesome allergy to mites and animal dander, disease in the upper airways including sinusitis and nonallergic rhinitis, uncontrolled asthma, pregnancy, breast-feeding, other illnesses, and drug abuse. Unfortunately, the required number of patients (60 according to the power calculation; see the Statistical Analysis section below) was not reached because of narrow inclusion criteria. The study was randomized, double-blind, placebo-controlled, and performed between 2013 and 2017. Before each treatment period, an assistant prepared sealed opaque envelopes for both active and placebo treatments to achieve a final 1:1 ratio. After the first year of the study, it was revealed that 3 actively treated patients had to be excluded and therefore, patients were randomized 2:1, active:placebo, for the remainder of the study to achieve the 1:1 ratio. The envelopes were randomly mixed, and an independent nurse drew 1 envelope for each patient and prepared the medical product according to the envelope at all 3 injection visits. The active allergen extracts could not be distinguished from placebo. Using this method, all the participants, physicians who administered the interventions, and study staff who evaluated the outcomes remained blinded until the follow-up visit after the first pollen season was completed.

Assessment of clinical parameters

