Clinical parameters were evaluated before the start of the treatment, in the fall after the first pollen season, and in the fall after the second pollen season (active group only). Treatment effect was evaluated by asking the patients to compare their allergic symptoms during the last pollen season with the pollen season before treatment on a visual analogue scale ranging from 0 (unchanged symptoms, no improvement) to 10 (total symptom relief, complete recovery). Asthma control 4 weeks before follow-up was estimated with the asthma control test, where a score of 19 or less suggests poorly controlled asthma.^{E1} Quality of life was assessed using the Juniper Asthma Quality of Life Questionnaire, giving a score ranging from 1 to 7, and a change in score of 0.5 points is considered clinically relevant.^{E2} Modified SSs and MSs^{E3} were calculated taking into account the frequency: daily (4 points); every second day (3 points); 1 to 3 days per week (2 points); occasionally (1 point); never (0 points), for the following symptoms: blocked nose, rhinorrhea, fatigue, sneezing, and asthma symptoms, and for the following medications used: local and systemic antihistamines, nasal steroids, asthma medication, and eye drops. A maximum score of 20 points for symptoms and 16 points for medication could be obtained.

Nasal provocation tests (NPTs) were performed with a commercially available birch or grass extract, Aquagen 100,000 SQ-E/mL (ALK-Abelló, Copenhagen, Denmark), according to a modified Lebel protocol.^{E4} One spray dose, 0.1 mL of the extract (10,000 SQ-E), was deposited in each nostril. Symptoms during NPTs were scored according to the Lebel scoring scale before and 5, 15, and 30 minutes after administration by a trained research nurse. The scoring system identifies nasal, eye, and ear symptoms: rhinorrhea, nasal pruritus, nasal congestion, ocular pruritus, watery eyes, and itchy ears, each graded on a scale from 0 to 3

points, and a total score was summarized after subtracting the starting score (maximum score is 54 + the number of sneezes).

Fraction of exhaled nitric oxide, FEV₁, and forced vital capacity were measured according to international guidelines.^{E5} Bronchial hyperresponsiveness to a challenge with methacholine was assessed, and the dose of methacholine causing a 20% reduction in FEV₁ (PD₂₀) was calculated.^{E6}

Assessment of serum antibodies

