Blood was taken at each visit, and serum and plasma were collected for immunological analyses. Allergen-specific IgE level was measured by ImmunoCAP (Phadia, Thermo Scientific, Uppsala, Sweden) for birch (t3) and timothy grass (g6) pollen according to the manufacturer's instructions. A cutoff level ≥ 0.35 kU_A/L was considered positive. In addition, IgG to birch/timothy grass pollen and IgG₄ to birch/timothy grass pollen were measured by ImmunoCAP, with the cutoff 2 mg/L for IgG and 0.05 mg/L for IgG₄.

Outcomes

The primary outcome of the study was the change in symptoms score after NPT. The secondary outcomes were SSs and MSs, changes in response to a bronchial challenge with methacholine (PD₂₀), treatment effect measured on a visual analogue scale, changes in quality of life, changes in allergen-specific serum immunoglobulin levels, incidence of adverse events, changes in asthma symptom scores, changes in pulmonary function measurement (FEV₁ and forced vital capacity), and changes in airway inflammation assessed by fraction of exhaled nitric oxide.

Adverse events and patient analysis

Four patients were removed or left the study before analysis of results; 3 patients (active group) were excluded after the first treatment period because of deviations from the treatment protocol, and 1 patient (placebo) left the study after the first treatment period, before the follow-up (see [Fig E1](#)).

No adrenaline was needed during the study. In total 91 injections were given, 55 with active treatment and 36 with placebo. A total of 69 mild side effects (pain, redness, itch or swelling at injection site, sneezing, and tiredness) within 24 hours after injection were reported. Fifty-nine of these were reported from 13 patients receiving active treatment, and 10 from 5 placebo-treated patients. In the active group, 1 patient suffered from generalized urticaria 15 minutes after injection and 1 patient reported increased asthma symptoms the day after injection.

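### The change that defines the primary NPT outcome has no stated reference point, and the available text does not use the pre-treatment NPT score as a covariate; unless the analysis section already adjusts for it, it should

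*Combined protocol and SAP*

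**What the plan says.** - **Outcomes:** "The primary outcome of the study was the change in symptoms score after NPT". The sentence gives no visit, no reference value and no method of comparing the arms.
- **Assessment of clinical parameters, timing:** "Clinical parameters were evaluated before the start of the treatment, in the fall after the first pollen season". The NPT is described under this heading, so a pre-treatment NPT score should exist alongside the first-fall score.
- **Assessment of clinical parameters, scoring:** for each NPT, "a total score was summarized after subtracting the starting score". Every NPT total is therefore already a change from the score just before the spray.
- **Outcomes, secondaries:** "The secondary outcomes were SSs and MSs, changes in response to a bronchial challenge with methacholine". Symptom and medication scores are named without the word change, while most other measures carry it.
- **Study outline, size:** "the required number of patients (60 according to the power calculation; see the Statistical Analysis section below) was not reached". The analysis section mentioned there is not in the available text.

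**The concern.** Two things are left open.

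**Meaning of change.** Because each NPT total already has its own starting score subtracted, the primary outcome could be the total at the first-fall visit alone. It could equally be the difference between that total and the pre-treatment total. These are different variables with different variances.

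**Use of the pre-treatment score.** Under the first meaning, an unadjusted comparison ignores the pre-treatment NPT. Under the second, it subtracts the whole pre-treatment score, which over-corrects when r is below 1. If the arms happen to differ by D at baseline, the unadjusted comparison is shifted on average by rD under the first meaning and by -(1-r)D under the second. A model with the pre-treatment score as covariate removes this shift under both.

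The trial did not reach its required 60 patients, so precision is scarce and chance baseline differences can be sizeable.

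**Working it through.** **The plan's own figure.** The available text gives no alpha, power, effect size or SD, so the 60 cannot be reproduced. It is used below only as a benchmark.

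**Number analysed (inferred).** The section on adverse events reports: "In total 91 injections were given, 55 with active treatment and 36 with placebo". The Study outline has the nurse who "prepared the medical product according to the envelope at all 3 injection visits", so three injections per patient are assumed.
- Active: 55/3 = 18.3. At no more than three each, 18 patients could receive only 54, so at least 19 were treated. Less 3 exclusions, this leaves 16.
- Placebo: 36/3 = 12. Less 1 withdrawal, this leaves 11.
- Analysed: 16 + 11 = 27. Rounding 18.3 down gives 15 + 11 = 26, with nearly the same results.

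**Assumptions.** The SD is s at both visits. The correlation r between the pre-treatment and first-fall scores is not documented, so 0.3, 0.5 and 0.7 are shown.

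**Per-patient variance that enters the arm difference**
- Unadjusted change from before to after treatment: 2s²(1-r)
- Unadjusted first-fall score: s²
- Covariate-adjusted (ANCOVA): s²(1-r²) × [1 + 1/(N-4)]. The bracket is the average cost of estimating the slope. At N = 27 it is 1 + 1/23 = 1.043.

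**Results at N = 27, in units of s²**

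| r | Change | Fall-only | ANCOVA | ANCOVA/change | ANCOVA/fall-only |
|---|---|---|---|---|---|
| 0.3 | 1.40 | 1.00 | 0.91 × 1.043 = 0.950 | 0.68 | 0.95 |
| 0.5 | 1.00 | 1.00 | 0.75 × 1.043 = 0.783 | 0.78 | 0.78 |
| 0.7 | 0.60 | 1.00 | 0.51 × 1.043 = 0.532 | 0.89 | 0.53 |

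Against the change score, the equivalent sample sizes are 27/0.678 = 39.8, 27/0.783 = 34.5 and 27/0.887 = 30.4. A simulation at 15 v 11 (20,000 runs per setting) gave variance ratios against the change score of 0.69, 0.79 and 0.89.

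**Where the gain ends**
- Against change: (1+r)/2 × 24/23 = 1 gives r = 2 × 23/24 - 1 = 0.917.
- Against fall-only: (1-r²) × 24/23 = 1 gives r² = 1/24, so r = 0.204.

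**Illustrative power.** This uses the noncentral t, 16 v 11, two-sided 0.05 and an assumed true difference of 1.0 SD of the fall score. The slope cost and the lost degree of freedom are included.

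| r | Change | Fall-only | ANCOVA |
|---|---|---|---|
| 0.3 | 55% | 69% | 71% |
| 0.5 | 69% | 69% | 79% |
| 0.7 | 89% | 69% | 92% |

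**Chance imbalance.** The SD of the baseline mean difference is s × sqrt(1/16 + 1/11) = 0.39s. The probability that it exceeds 0.5s in either direction is about 0.20. At D = 0.5s and r = 0.5, the shift is 0.5 × 0.5s = 0.25s upward for fall-only and 0.25s downward for the change score.

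**The case against.** **The analysis method cannot be seen.** The document tells the reader to "see the Statistical Analysis section below", and that section is not in the available text. A reader might infer that the trial compares raw changes and so gives up precision. Nothing available shows an unadjusted test, and the gap cannot be held against the plan. This stands, and it makes the point conditional.

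**A change outcome does not exclude adjustment.** Modelling the change with the pre-treatment score as covariate gives the same treatment estimate and standard error as modelling the fall score with that covariate. Naming the outcome a change therefore loses nothing in itself. This stands too.

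**The gain is neither certain nor free.** It depends on an undocumented r and on which meaning of change applies. At r = 0.7 power moves only from 89% to 92% against a change score, and at r = 0.3 only from 69% to 71% against fall-only. It is tempting to say that ANCOVA is never less precise than either alternative, but at this size that fails above r of about 0.92 and below about 0.2. The 1.0 SD effect is illustrative, and equal variances are assumed.

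**Secondary outcomes.** A reader might infer that symptom and medication scores are compared as unadjusted levels. The list only names them and does not say how they are compared.

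**Timing.** The document is dated November 2019, after a trial that ran to 2017 and whose blinding was kept only until first-season follow-up was complete. A model chosen now would be chosen after unblinding. That limits how a changed analysis may be presented, but does not remove the need to define the outcome.

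**Conclusion.** The point holds as a conditional one. The primary outcome sentence does not say which change is meant or at which visit, and the available text does not use the pre-treatment NPT score as a covariate. If the analysis section already adjusts for it, only the outcome wording needs attention. If it does not, adjustment would reduce the variance of the primary comparison by 11% to 32% against a change score, or by 5% to 47% against fall-only, over r from 0.3 to 0.7. These figures rest on about 27 analysed patients inferred from injection counts, equal variances at both visits and an assumed r. The documents do not support the stronger claim that the trial has in fact lost this precision.

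**What to change.** 1. In Outcomes, define the NPT change: which score, at which visit, relative to what.
2. Check the Statistical Analysis section. If it already adjusts for the pre-treatment NPT score, align the outcome wording with it.
3. If it does not, state the primary analysis as the active-minus-placebo difference in first-fall NPT score from a linear model with arm and pre-treatment NPT score, reported with its 95% confidence interval. If the distribution calls for a rank method, use rank ANCOVA with the same covariate.
4. Use the same form for each secondary with a pre-treatment value, including the symptom and medication scores.
5. Label any model adopted now as specified after unblinding, and report it beside the analysis originally planned.

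**Cost:** a few sentences, one degree of freedom and about 4% of variance for estimating the slope. No new data, visits or patients are needed. Reporting r from the trial's own data would show which part of the range applies.

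### Three treated active patients were excluded before analysis, so the comparison described is per-protocol in type, not as randomised

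*Combined protocol and SAP*

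**What the plan says.** Under the heading Adverse events and patient analysis, the combined protocol and SAP reports: "Four patients were removed or left the study before analysis of results". Of these, "3 patients (active group) were excluded after the first treatment period because of deviations from the treatment protocol". The fourth was a placebo patient who left before follow-up. The same section counts 91 injections, 55 active and 36 placebo.

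The Study outline adds that after the first year "it was revealed that 3 actively treated patients had to be excluded", and that in consequence "patients were randomized 2:1, active:placebo, for the remainder of the study to achieve the 1:1 ratio". On procedure it says: "Before each treatment period, an assistant prepared sealed opaque envelopes for both active and placebo treatments". A nurse then drew one envelope per patient and "prepared the medical product according to the envelope at all 3 injection visits". Participants, treating physicians and outcome assessors "remained blinded until the follow-up visit after the first pollen season was completed".

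The Outcomes section makes the change in symptom score after the nasal provocation test (NPT) the primary outcome. For the power calculation the reader is told to "see the Statistical Analysis section below". Neither that section nor Fig E1, which is cited for the patient losses, is in the available text.

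**The concern.** Randomisation makes the two groups comparable as assigned. Once treated patients are taken out of one arm for something that happened after assignment, the remaining active patients are a selected subset, and the design no longer guarantees comparability. Patients who depart from a treatment schedule may differ in tolerance, adherence or disease severity, and so in how their NPT score would have changed.

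Here the removals for deviation all fall in the active arm, and the trial fell short of its planned 60 patients, so three patients carry appreciable weight. Raising the active share to 2:1 afterwards brings in new active patients. It does not put back the ones removed.

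The available text also does not say what the deviations were, which role decided on exclusion, or whether the decision came before or after first-year unblinding. A reader needs these facts to judge how far the exclusions could matter.

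**Working it through.** **Inputs.** From Adverse events and patient analysis: 3 active exclusions, 1 placebo withdrawal, 55 active and 36 placebo injections. From Study outline: three injection visits, planned size 60.

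**1. The document's own counts.** 3 + 1 = 4 patients lost and 55 + 36 = 91 injections; both agree with the text. The 60 cannot be recomputed, because no alpha, power, effect size or SD is in the available text. Nothing below uses it.

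**2. Share of the active arm removed.** This is inferred, assuming at most three injections per patient (one at each visit).
- If the 55 include the excluded patients: 55/3 = 18.3, so at least 19 active patients, and 3/19 = 15.8%.
- If the 55 omit them: at least 19 + 3 = 22, and 3/22 = 13.6%.
- Since 55 is not a multiple of 3, at least one active course was incomplete, and more incomplete courses mean a larger arm. At an average of 2 injections: 55/2 = 27.5, so 28 patients (3/28 = 10.7%), or 28 + 3 = 31 (3/31 = 9.7%).

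So about 16% is the ceiling under the stated assumption, and about 10% is what an average of two injections would give.

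**3. Placebo arm, on three injections each.** 36/3 = 12 patients, or 13 if the withdrawal is outside the count. None was excluded for deviation; 1/12 = 8.3% or 1/13 = 7.7% was lost by leaving.

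**4. What the removal could do to the active mean.** Let n be the active patients randomised and d the mean NPT change in the retained patients minus the mean in the three excluded. The full-arm mean is [(n − 3) × retained mean + 3 × excluded mean]/n, so the retained mean differs from it by (3/n) × d. The documents give no value for d, so a range is assumed:
- d = 0: no shift.
- d = ±1 SD: 0.158 SD either way at n = 19, 0.136 SD at n = 22, and 0.107 to 0.097 SD at n = 28 to 31.

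**5. One illustration.** Suppose the three would have changed as placebo did, and the placebo withdrawal as the retained placebo patients did. The full effect is then (n − 3)/n of the exclusion-based one, which is overstated by n/(n − 3): 19/16 = 1.19 or 22/19 = 1.16. If the three would have changed like the retained active patients, the factor is 1.

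**6. Could 3 against 0 be chance?** For 19 to 22 active and 12 or 13 placebo patients, the two-sided Fisher p-value lies between about 0.25 and 0.54, so yes. The point concerns exclusion after randomisation. It does not claim that deviations were more frequent on active treatment.

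**The case against.** The strongest reply is that the analysis population has not been seen. The Statistical Analysis section may define an as-randomised analysis, and Fig E1 may give the reasons for exclusion. That stands: a reader might infer that no such analysis was planned, and the available text does not support this. It does not undo the stated fact that three treated patients were removed before the results were analysed.

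A reader might also infer that the exclusions were made with knowledge of allocation or outcome. The documents do not show this. The stated reason concerns treatment, not response. Blinding is claimed up to the first-season follow-up, and allocation was handled by an assistant and an independent nurse, so the ratio could be changed without unblinding the assessors. The two descriptions of timing (after the first treatment period, after the first year) leave the order of events open. That justifies a question and nothing stronger.

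The likely impact may be modest. With 16 against 11 analysed (19 − 3 and 12 − 1), the standard error of the arm difference is √(1/16 + 1/11) = 0.39 SD, well above the 0.16 SD shift, which itself needs an assumed 1 SD difference. This is fair, but a possible systematic shift is a different matter from sampling error and is not covered by the confidence interval.

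Finally, the change to 2:1 after year 1 ties arm to treatment year, and a reader might infer a calendar-year bias. No year effect on the NPT is shown, the test uses a fixed dose in the fall, and year-1 counts by arm are not given. Arm sizes compatible with the injection counts lead to different year splits, so no figure for this is defensible.

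**Conclusion.** The point holds in a limited form. Three randomised and treated active patients were removed before analysis for treatment deviations, and no placebo patient was removed for that reason. The comparison described is of a per-protocol type, and the later 2:1 allocation does not make it as randomised. The placebo set is also incomplete by one withdrawal.

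The share removed is an inference, and more than one injection per visit would raise the ceiling given above. Whether the treatment effect is biased, in which direction and by how much, cannot be determined. The statement that the trial overstates the benefit of active treatment is not supported; it holds only under assumptions such as the illustration in step 5. This should be fixed, with medium confidence, because the exclusions are stated outright while the analysis section is unseen.

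**What to change.** First check the Statistical Analysis section and Fig E1. Unless they already provide it:

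- Report an as-randomised analysis of the NPT change, with the three excluded active patients and the placebo withdrawal in their assigned arms. Label the exclusion-based result as per-protocol.
- Use observed follow-up NPT scores where they exist. Where they are missing, show a sensitivity range, for example by imputing from the placebo arm. Full-scale bounds will not work: Assessment of clinical parameters sets the maximum at 54 (6 symptoms × 3 points × 3 time points) plus a sneeze count with no stated cap, so the score has no finite maximum.
- For each exclusion, state the reason, the timing relative to unblinding and the role that decided.
- Because the ratio changed after year 1, an adjustment for year 1 versus later may be shown as a secondary sensitivity analysis.

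The cost is one small re-analysis and a short account of three exclusions. The trial is complete, so an analysis added now should be identified as such. The estimate may be less favourable to active treatment and less precise, and if the three have no follow-up NPT it will rest partly on assumptions about them.
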